13.5 Interim Analysis

There is no interim analysis planned. Serious adverse events will be monitored by the committee on an ongoing basis throughout the study.

13.6 Sample Size and Randomization

Bellamy demonstrated in his paper from 2007 (table 3) that a BLISS response at any time during the study was achieved in 70% receiving appropriate care and Hylan G-F 20 and only in 38% of patients receiving appropriate care ($P < 0.0001$). A power calculation using a one-sample comparison of proportion with hypothesized value sample size was performed to determine non-inferiority to the 70% results quoted by Bellamy. Power calculations were measured using STATA's SAMPSI calculator. If we postulate a 20% non-inferiority limit (i.e. that at least 50% of patients receiving G-F 20 will achieve a BLISS response), the sample size required to have 90% power and $\alpha = 0.025$ to show non-inferiority at 50% would be 70. For a 10% non-inferiority limit with 90% power and $\alpha = 0.025$, the required sample size is 274, and for 15% non-inferiority limit with 90% power and $\alpha = 0.025$, it is 124 patients. These numbers do not allow for dropouts, therefore, we intend to recruit 150 subjects to account for dropout.

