| SAFETY EVALUATIONS | 
The repeat treatment phase evaluated the safety profile of a second injection of Synvisc-One. One hundred and sixty patients were treated during this phase of the study, of which 77 patients received a second injection of Synvisc-One. These patients were followed for 4 weeks and out of 77 patients, only 4 (5.2%) experienced device-related AEs in the injected knee. All such events were mild to moderate and were treated symptomatically. Patients who developed injected knee AEs during the initial phase of the study, and who subsequently received repeat treatment, did not experience injected knee AEs upon repeat exposure to Synvisc-One.
 |
| PLANNED INTERIM ANALYSES | 
There is no interim analysis planned. Serious adverse events will be monitored by the committee on an ongoing basis throughout the study.
 |

| | |
|---|---|
| 
STATISTICS Primary Analysis Endpoint
 | 
The primary endpoint for the study will be analyzed using a responder analysis. The proportion of responders following injection within the 6 months following the baseline injection will be calculated based on Worst Knee Pain scores ≤ 3 on a 0-10 pain scale, which is a threshold consistent with other similar studies (Tubach 2005, Bellamy 2010). The primary endpoint is defined as non-inferiority of the proportion of responders in our study relative to an external criterion for the responder proportion (Bellamy 2010). Bellamy demonstrated in his paper from 2007 (table 3) that a BLISS response at any time during the study was achieved in 70% receiving appropriate care and Hylan G-F 20 and only in 38% of patients receiving appropriate care ($P < 0.0001$). We propose a non-inferiority delta of 20% relative to this external criterion, and thus the primary endpoint will be tested by a test of our sample proportion (p) with null hypothesis $H_0: p < 0.50$ vs. alternative hypothesis $H_1: p \geq 0.50$. This test will be performed using the Wilson-Agresti method for testing a single binomial proportion at a one-sided significance level of 0.025 (i.e. non-inferiority will be satisfied if the 95% Wilson-Agresti (REF BROWN ET AL 2001) interval for the proportion of responders excludes the null rate of 0.50).
 |

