| 
STATISTICS Secondary Endpoints
 | 
For subsequent injections, duration of response over time and median duration of response will be estimated using survival analysis techniques. Inference for activity levels and quality of life will focus on changes from baseline to 3 months. We will examine the time course for the longitudinal data on pain score, activity level, and quality of life measures across the three years of the study using mixed effects models.
 |
| 
Rationale for Number of Subjects
 | 
Power Calculation
 
Bellamy demonstrated in his paper from 2007 (table 3) that a BLISS response at any time during the study was achieved in 70% receiving appropriate care and Hylan G-F 20 and only in 38% of patients receiving appropriate care ($P < 0.0001$). A power calculation using a one-sample comparison of proportion with hypothesized value sample size was performed to determine non-inferiority to the 70% results quoted by Bellamy. Power calculations were measured using STATA's SAMPSI calculator. If we postulate a 20% non-inferiority limit (i.e. that at least 50% of patients receiving G-F 20 will achieve a BLISS response), the sample size required to have 90% power and
 |

| | |
|------------------------------------|--|
| | 
$\alpha=0.025$ to show non-inferiority at 50% would be 70. For a 10% non-inferiority limit with 90% power and $\alpha=0.025$, the required sample size is 274, and for 15% non-inferiority limit with 90% power and $\alpha=0.025$, it is 124 patients. These numbers do not allow for dropouts, therefore, we intend to recruit 150 subjects to account for dropout.
 
Conservatively assuming a 20% rate of drop-out, the resulting sample size of $n=120$ has better than 90% power (one sided test with $\alpha=0.025$) to show non-inferiority assuming the true responder rate is 65% (i.e. not quite as high as the 70% external reference).
 |
| 
DATA MANAGEMENT PLAN
 | 
Data management and analysis for the study will be performed by the Biostatistics Consulting Unit (BCU) of UCSF’s Clinical and Translational Science Institute (CTSI). Data will be stored on a HIPAA-compliant server. The server room has state-of-the-art environmental controls and security features and is protected by a firewall and anti-virus software.
 |

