13 STATISTICAL METHODS AND CONSIDERATIONS

Prior to the analysis of the final study data, a detailed Statistical Analysis Plan (SAP) will be written describing all analyses that will be performed. The SAP will contain any modifications to the analysis plan described below.

Data Sets Analyzed

The primary endpoint is based on a responder analysis. Response is defined as maintaining a Worst Knee Pain score ≤ 3 on a 0-10 pain scale throughout the 6 months following the baseline injection. Trial success will be based on a non-inferiority test (with 20% non-inferiority threshold) of this response rate in comparison to an external criterion of 70% (Bellamy 2010). Secondary endpoints include determining the duration of response after subsequent injection, determining the effects of treatment on activity levels and quality of life, and describing the three-year time course of each of the study endpoints. The sample size will be $n=150$ subjects followed for up to 3 years after baseline injection. The power to conclude non-inferiority for a true response rate of 65% is better than 92%.

Demographic and Baseline Characteristics

The following demographic variables at screening will be summarized by: race, gender, age, height and weight.

Analysis of Primary Endpoint

The primary endpoint for the study will be analyzed using a responder analysis. The proportion of responders following injection within the 6 months following the baseline injection will be calculated based on Worst Knee Pain scores ≤ 3 on a 0-10 pain scale, which is a threshold consistent with other similar studies (Tubach 2005, Bellamy 2010). The primary endpoint is defined as non-inferiority (with 20% non-inferiority threshold) of the proportion of responders in our study relative to an external criterion of 70% for the responder proportion (Bellamy 2010).

Primary Statistical Analysis: Define the true probability of a subject being a responder as π and the non-inferiority threshold $\delta_{NI} = 0.20$. We require the test of

$$H_0: \pi < 0.70 - \delta_{NI} = 0.50$$

vs. the alternative

$$H_1: \pi \geq 0.70 - \delta_{NI} = 0.50.$$

Non-inferiority will be accepted if the null hypothesis can be rejected with a 2.5% one-sided type I error. To test this hypothesis, we will use the Wilson-Agresti method for a single binomial proportion. Non inferiority will be accepted if the 95% Wilson-Agresti (REF BROWN ET AL 2001) interval for the proportion of responders excludes the null rate of 0.50.

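### The sample sizes 70, 124 and 274 come from a different test than the one planned (on the safe side), and the n=150 power cells of 72% and 97% should read 66% and 96%

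*Combined protocol and SAP*

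**What the plan says.** The primary test is defined in Section 13, Analysis of Primary Endpoint. The responder proportion is judged "relative to an external criterion of 70% for the responder proportion" with a margin of 0.20, so the null rate is 0.50. On the error rate the section says: "Non-inferiority will be accepted if the null hypothesis can be rejected with a 2.5% one-sided type I error". On the method it says "we will use the Wilson-Agresti method for a single binomial proportion", with success if the 95% "interval for the proportion of responders excludes the null rate of 0.50". The Synopsis (Statistics, Primary Analysis Endpoint) describes the same test: "Wilson-Agresti method for testing a single binomial proportion at a one-sided significance level of 0.025".

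Section 13.6 and the Synopsis (Rationale for Number of Subjects) give sizes for 90% power at alpha 0.025: for the 20% margin, the number "to show non-inferiority at 50% would be 70"; for 15%, 124; for 10%, 274. Sidedness is not stated for these three. The Synopsis then adds that n=120, after 20% dropout from 150, "has better than 90% power (one sided test with" alpha 0.025) at a true rate of 65%.

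The power table in Section 13, Operating Characteristics, gives 72% (n=150) and 61% (n=120) at a true rate of 0.60, and 97% and 92% at 0.65. All cells at 0.70 and 0.75 are above 99%.

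**The concern.** A stated sample size or power should follow from the test that will be run. Here two sets of figures do not.

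The three sizes carry the label alpha 0.025 and stand beside a calculation that is explicitly one-sided at 0.025, yet they are larger than a one-sided 0.025 test needs. In the power table, the n=120 column agrees with the planned interval rule but the n=150 column does not.

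Section 13 promises a detailed SAP before the final analysis. Its author could carry forward a reversed null, a two-sided alpha, and a table implying that 87 responders out of 150 is a success when the written rule says it is not.

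**Working it through.** **Inputs.** Reference rate 0.70; margins 0.20, 0.15 and 0.10; one-sided alpha 0.025; success if the 95% Wilson-Agresti interval excludes 0.50 (Section 13). Power 90%; stated sizes 70, 124 and 274 (Section 13.6). Power cells from the Operating Characteristics table. Section 13.6 does not name the true rate behind its sizes; I take it as 0.70, the reference rate.

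**Part 1: sample sizes**

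n = [(z_a·√(p0(1−p0)) + z_b·√(p1(1−p1))) / (p1 − p0)]², with z_b = 1.2816 for 90% power, rounded up.

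Plan's figure for the 20% margin, reproduced with null 0.70, alternative 0.50 and two-sided 0.025 (z_a = 2.2414):
[(2.2414 × 0.4583 + 1.2816 × 0.5) / 0.20]² = 69.55, so 70.

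Planned test, with null 0.50, true rate 0.70 and one-sided 0.025 (z_a = 1.960):
[(1.960 × 0.5 + 1.2816 × 0.4583) / 0.20]² = 61.41, so 62.

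All four combinations:

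| Null | Alpha 0.025 | 20% margin | 15% margin | 10% margin |
|---|---|---|---|---|
| 0.70 | two-sided | 69.55 → **70** | 123.17 → **124** | 273.89 → **274** |
| 0.70 − margin | one-sided (planned) | 61.41 → 62 | 108.49 → 109 | 239.46 → 240 |
| 0.70 − margin | two-sided | 72.93 → 73 | 128.80 → 129 | 284.04 → 285 |
| 0.70 | one-sided | 59.21 → 60 | 104.82 → 105 | 232.87 → 233 |

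Only the first row matches the plan, and it does so three times out of three. Correcting one input alone does not reach the planned test, so both the direction and the alpha differ from it. Excess over the planned-test formula: 70/62 = 1.13, 124/109 = 1.14, 274/240 = 1.14.

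Exact binomial power of the Wilson rule at the stated sizes, true rate 0.70:

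| n | Null | Cut-off | Power |
|---|---|---|---|
| 70 | 0.50 | 44 | 92.2% |
| 124 | 0.55 | 80 | 92.2% |
| 274 | 0.60 | 181 | 93.1% |

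At the formula sizes 62, 109 and 240, exact Wilson power is 91.1%, 88.6% and 90.9%. It stays at or above 90% from n = 64, 115 and 246 (checked up to n=399).

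**Part 2: power table**

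Wilson lower limit = [p + z²/2n − z·√(p(1−p)/n + z²/4n²)] / (1 + z²/n), z = 1.95996.

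| Responders / n | Wilson lower limit | Agresti-Coull lower limit | Excludes 0.50? |
|---|---|---|---|
| 87 / 150 | 0.499985 | 0.499960 | no |
| 88 / 150 | 0.506659 | 0.506629 | yes |
| 70 / 120 | 0.493880 | 0.493843 | no |
| 71 / 120 | 0.502208 | 0.502163 | yes |

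The score statistic gives the same answer for 87: (0.58 − 0.50) / √(0.25/150) = 1.95959, just short of 1.95996. The cut-offs are therefore 88 and 71 under either reading of Wilson-Agresti.

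Exact power, P(X ≥ cut-off):

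| n, cut-off | True rate 0.60 | True rate 0.65 | Plan states |
|---|---|---|---|
| 150, 87 | 72.1% | 96.9% | 72%, 97% |
| 150, 88 (planned rule) | 66.3% | 95.5% | – |
| 120, 71 (planned rule) | 61.2% | 92.3% | 61%, 92% |

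The printed n=150 cells match a cut-off of 87. Normal approximations do not explain them: at n=150 they give 69.1% and 96.4% with null variance, or 70.5% and 97.1% with alternative variance. A cut-off of 87 would follow from a Wald or Jeffreys interval, or from treating the near-tie as a success; the documents do not say which. At a true rate of 0.70, power with cut-off 88 is 99.9%, so the cells above 99% stand.

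**The case against.** The strongest reply is that nothing depends on these figures. The stated sizes exceed what 90% power needs, and the argument for enrolling 150 rests on n=120 with 92% power at a true rate of 0.65, which reproduces. The statement in Section 13 of better than 92% power at 65% also holds. All of this stands, and it limits the point to a reporting correction.

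The reversed null and two-sided alpha are inferred from matching outputs, since no software input is shown. That is fair, although a match on all three sizes makes coincidence unlikely. Whatever the inputs were, 70, 124 and 274 are not the planned test's sizes.

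The formula sizes are not clean replacements either: 109 gives only 88.6% exact power. Against the exact-rule sizes of 64, 115 and 246 the excess is smaller, about 9%, 8% and 11%. This also stands, and it is why the stated sizes should be relabelled and not replaced.

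Finally, 87 against 88 is a near-tie, and power is jagged in n: at a true rate of 0.60 it is 68.8% at n=149, 66.3% at 150 and 69.8% at 151. The change from 97% to 96% is minor, and the plan makes no adequacy claim at 0.60. But the rule requires 0.50 to be excluded, and a limit of 0.499985 does not exclude it. The case against 87 rests on that rule and not on exact type I error. Cut-off 87 has exact error 0.0300, but the correct cut-off of 71 at n=120 also slightly exceeds 0.025 (0.0274), which is ordinary discreteness.

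**Conclusion.** The concern holds in both parts.

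- The sizes 70, 124 and 274 are not those required for 90% power under the planned test. They are 13%, 14% and 14% above its normal-approximation sizes and have exact Wilson power of 92.2%, 92.2% and 93.1%. The error is conservative.
- At n=150, power is 66.3% and not 72% at a true rate of 0.60 (5.8 points by the unrounded figures), and 95.5% and not 97% at 0.65 (about 1.5 points). Only the first difference is material.

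This assumes a true rate of 0.70 behind the sample sizes, exact binomial power, and the success rule read literally. It does not depend on whether Wilson-Agresti means the Wilson or the Agresti-Coull interval. The n=120 column, the cells above 99% and the choice of 150 subjects are sound, and no design decision changes.

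**What to change.** 1. In the Operating Characteristics table of Section 13, change the n=150 cells to 66% (true rate 0.60) and 96% (0.65). State the cut-offs beside the table: the lower limit exceeds 0.50 with at least 88 responders if n=150, or 71 if n=120.
2. In Section 13.6 and the Synopsis rationale, state the inputs: null equal to 0.70 minus the margin, assumed true rate 0.70, one-sided alpha 0.025.
3. Keep 70, 124 and 274, but describe them as sizes with exact Wilson power of 92%, 92% and 93%, and no longer as the sizes required for 90%. If 62, 109 and 240 are also quoted, label them as normal-approximation values.
4. Keep the enrolment target of 150.

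The cost is wording only. Two published power figures become lower; enrolment, the test and the decision rule do not change.

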14 DATA COLLECTION, RETENTION AND MONITORING

Data Collection Instruments

Study personnel will enter data into REDCap (Research Electronic Data Capture). REDCap is a secure, web-based application designed to support data capture for research studies. Subjects will not be identified by name in the study database, but will be identified by a subject number and initials.

14.2 Data Management Procedures

Once data has been successfully entered into the database, the Biostatistics Consulting Unit (BCU) of UCSF's Clinical and Translational Science Institute (CTSI) will perform data management and analysis for the study. Most CTSI personnel have office space within the area occupied by the Department of Epidemiology and Biostatistics at China Basin Landing near UCSF's Mission Bay campus, along with desktop computers and access to departmental "cloud" computing resources. These include secure data storage and access on a HIPAA-compliant server, along with SAS and Stata statistical software. The server room has state-of-the-art environmental controls and security features that include secure, limited access and alarm systems; floor-mount, locking server racks with built-in AC and mounted power strips; dedicated AC unit with temperature monitoring; dedicated circuit breaker and power distribution units; uninterruptible power supply equipment; and fire detection and suppression. Servers are protected by a firewall and anti-virus software. Files and databases are backed up daily. Back-up tapes are sent to an off-site record storage facility every two weeks, with a 2-month tape rotation.

Access to network resources is granted based on documented authorization from a supervisor and permissions are based on user responsibilities. Each user is given a network account consisting of a unique username and a user-designated password that must meet network security criteria. Before network access is given, users are required to train on university electronic security policies. All procedures for the handling and analysis of data will be conducted using good computing practices meeting FDA guidelines for the handling and analysis of data for clinical trials.

Data Quality Control and Reporting

After data have been entered into the study database, a system of computerized data validation checks will be implemented and applied to the database on a regular basis. The study database will be updated in accordance with the resolved queries. All changes to the study database will be documented.

14.4 Archival of Data

The database is safeguarded against unauthorized access by established security procedures; appropriate backup copies of the database and related software files will be maintained. Databases are backed up by the database administrator in conjunction with any updates or changes to the database.

At critical junctures of the protocol (e.g., production of interim reports and final reports), data for analysis is locked and cleaned per established procedures.

Availability and Retention of Investigational Records

The Investigator must make study data accessible to the monitor, other authorized representatives of the Sponsor (or designee), IRB, and Regulatory Agency (e.g., FDA) inspectors upon request. A file for each subject must be maintained that includes the signed Informed Consent, HIPAA Authorization and Assent Form and copies of all source documentation related to that subject. The Investigator must ensure the reliability and availability of source documents from which the information on the CRF was derived.

All study documents will be kept secured for a period of two years following marketing of the investigational product or for two years after centers have been notified that the IND has been discontinued.

14.6 Monitoring

Monitoring will be conducted by representatives of the Sponsor according to the U.S. CFR Title 21 Parts 50, 56, and 312 and ICH Guidelines for GCP (E6).

Subject Confidentiality

In order to maintain subject confidentiality, only a subject number and subject initials will identify all study subjects on study documentation.

15 ADMINISTRATIVE, ETHICAL, REGULATORY CONSIDERATIONS

The study will be conducted according to the Declaration of Helsinki, Protection of Human Volunteers (21 CFR 50), Institutional Review Boards (21 CFR 56), and Obligations of Clinical Investigators (21 CFR 312).

To maintain confidentiality, all laboratory specimens, evaluation forms, reports and other records will be identified by a coded number and initials only. All study records will be kept in a locked file cabinet and code sheets linking a patient's name to a patient identification number will be stored separately in another locked file cabinet. Clinical information will not be released without written permission of the subject, except as necessary for monitoring by the FDA. The Investigator must also comply with all

applicable privacy regulations (e.g., Health Insurance Portability and Accountability Act of 1996, EU Data Protection Directive 95/46/EC).

Protocol Amendments

Any amendment to the protocol will be submitted by [name] prior to implementation. Protocol amendments cannot be implemented without prior written IRB approval except as necessary to eliminate immediate safety hazards to patients. A protocol amendment intended to eliminate an apparent immediate hazard to patients may be implemented immediately, provided the IRBs are notified within five working days.

15.2 Institutional Review Boards and Independent Ethics Committees

The protocol and consent form has been approved by the will be reviewed and approved by the IRB of the center prior to study initiation. Serious adverse experiences regardless of causality will be reported to the IRB in accordance with the standard operating procedures and policies of the IRB, and the Investigator will keep the IRB informed as to the progress of the study. The Investigator will obtain assurance of IRB compliance with regulations.

Any documents that the IRB may need to fulfill its responsibilities (such as protocol, protocol amendments, Investigator's Brochure, consent forms, information concerning patient recruitment, payment or compensation procedures, or other pertinent information) will be submitted to the IRB. The IRB's written unconditional approval of the study protocol and the informed consent form will be in the possession of the Investigator before the study is initiated. The IRB's unconditional approval statement will be transmitted by the Investigator to Genzyme prior to the shipment of study supplies to the site. This approval must refer to the study by exact protocol title and number and should identify the documents reviewed and the date of review.

Protocol and/or informed consent modifications or changes may not be initiated without prior written IRB approval except when necessary to eliminate immediate hazards to the patients or when the change(s) involves only logistical or administrative aspects of the study. Such modifications will be submitted to the IRB and written verification that the modification was submitted and subsequently approved should be obtained.

The IRB must be informed of revisions to other documents originally submitted for review; serious and/or unexpected adverse experiences occurring during the study in accordance with the standard operating procedures and policies of the IRB; new information that may affect adversely the safety of the patients of the conduct of the study; an annual update and/or request for re-approval; and when the study has been completed.

